# **Protocol History/Amendment Summary\***

Version number	Release date	Comments
1.0	12 December 2022	Initial version
2.0	25 May 2023	Change in signatory for "Deputy Director, Pandemic Threats".
		Updated "date of symptom onset" to "duration of symptom" throughout protocol.
		Updated study site from "Royal Free Hospital London" to "Liverpool School of Tropical Medicine" throughout protocol.
		Changed inclusion criteria to "Individuals ≥ 2 years of age"
		Added more detail on general blinding, screening, and enrolment procedures.
		Clarified number of samples collected per sample type.
		Inclusion of blood as a sample type for exploratory analysis.
		Added "VTM/UTM" for collection of skin lesion and oropharyngeal swabs.
		Included interim analysis when enrolment reaches 50 participants to recalculate sample size for screening.

# **List of Abbreviations and Acronyms**

Abbreviation/acronym	Meaning
AE	Adverse Event
Ag	Antigen
CRF	Case Report Form
Ct	Cycle time
GCP	Good Clinical Practice
GCLP	Good Clinical Laboratory Practice
GDoP	Good Documentation Practice
ICF	Informed Consent Form
ICH	International Council on Harmonisation
IDMC	Independent Data-Monitoring Committee
IEC	Independent Ethics Committee
IRB	Institutional Review Board
INRB	Institut National de Recherche Biomédicale
ISF	Investigator Site File
ISO	International Organisation for Standardization
MPXV	Mpox virus
NPA	Negative percent agreement
PCR	Polymerase chain reaction
POC	Point of care
PPA	Positive percent agreement
QA	Quality Assurance
QC	Quality Control
QMS	Quality Management System
RA	Regulatory Authority
RBM	Risk Based Monitoring
RM	Risk Management
SAE	Serious Adverse Event

Performance evaluation of Mpox point-of-care diagnostics

Protocol #PP008 Page 10 of 40

SAP	Statistical Analysis Plan
SOA	Schedule of Activities
SOP	Standard Operating Procedure
TMF	Study Master File
UTM	Universal Transport Media
VTM	Viral Transport Media
WHO	World Health Organisation

# **Protocol Synopsis**

Title	Evaluation of the performance of rapid point-of-care diagnostics for Mpox virus			
Short title	Performance evaluation of MpoX point of care diagnostics			
Protocol version and date	Version 2.0 – 25 May 2023 These parts may be adapted in site-specific protocol			
Background and rationale	The aim of this study is to independently evaluate the diagnostic performance of rapid, point-of-care (POC) assays for the direct detection of Mpox antigens (Ag) or DNA in comparison to laboratory-based PCR, which is the current gold standard for the confirmatory testing of Mpoxinfection.			
	Mpox is a viral disease of zoonotic origin with symptoms similar to those seen in patients with smallpox, although clinically less severe. Since the eradication of smallpox in the 70s, mpox outbreaks have been reported in multiple countries in West and Central Africa; however, the true burden is unknown (1). There are two known clades of mpox virus, one endemic in Western Africa (clade II) and one in the Congo Basin region (clade I), the latter causing more severe illness. The Democratic Republic of Congo (DRC) reports the highest number of cases per year; since 2010, over 1,500 cases and 150-250 deaths have been reported per year, with a mortality rate around 10%. Cases continue to be regularly reported in the region, sustained by sporadic zoonotic and human-to-human transmissions.			
	In May 2022, multiple cases of mpox were identified in several non-endemic countries. This multi-country outbreak was declared a Public Health Event of International Concern by the IHR Emergency Committee on July 23 rd , 2022. As of November 13 th , 2022, there have been 79,411 laboratory confirmed cases and 50 deaths reported to WHO from 110 countries/territories in the six WHO regions, with the majority being reported from the WHO region of the Americas. Actual case numbers are likely to be underestimated, due to the lack of early clinical recognition of the disease in non-endemic regions as cases are often atypical to those described in previous outbreaks, limited surveillance mechanisms, and the lack of available laboratory diagnostics, among other factors.			
	PCR on skin lesion material is the recommended method for confirmation of mpox infection. However, in regions with limited PCR testing capacity or rapid access to results, POC tests for mpox, if shown to have sufficient accuracy to aid in clinical decision-making, could contribute substantially to control of disease spread and improved patient management. POC tests might provide the only source of rapid diagnostic testing in resource limited and decentralized settings where reference testing via PCR is a challenge.			
Primary objective(s)	1.1. To determine the diagnostic accuracy of mpox POC Ag or POC/near-POC molecular tests (index tests) on skin lesion specimens vs. gold-standard PCR (reference test).			
Secondary objective(s)	2.1. To determine the association of index test sensitivity/positive percent agreement (PPA) results with disease stage (days since onset of symptoms, e.g. acute, early, late) and Ct values (as a proxy for viral load)			
	

2.2. To compare performance of mpox POC test results on skin lesion specimens by the following subgroups (where information is available):

Sex

			

Performance evaluation of Mpox point-of-care diagnostics

Protocol #PP008 Page 12 of 40

	· Virus clade		
	· Age group		
	Vaccination status (e.g. smallpox vaccination)		
Exploratory objectives	3.1 To determine the diagnostic performance of mpox POC and near-POC antigen/molecular tests on other specimen types (e.g. respiratory swabs, whole blood/ plasma ) vs. gold-standard PCR on lesion specimens		
	3.2 To determine the diagnostic performance of mpox POC and near-POC antigen/molecular tests on other specimen types (e.g. respiratory swabs, whole blood/ plasma ) vs. gold-standard PCR on the respective specimen.		
Primary endpoints (outcomes)  1.1. Point estimates of clinical sensitivity/PPA and specificity/negative pagreement (NPA) of index test, with 95% confidence intervals, using a PCR as reference standard.			
Secondary endpoints	2.1. Point estimates of sensitivity/PPA stratified by duration of symptoms, Ct values of the reference PCR test.		
(outcomes)	2.2. Point estimates of sensitivity/PPA and specificity/NPA with 95% confidence intervals stratified by the specified subgroups.		
Exploratory endpoints (outcomes)	3.1 Point estimates of sensitivity/PPA and specificity/NPA of index test on alternative specimen types, with 95% confidence intervals, using a lab-based PCR on lesion samples as reference standard		
	3.2 Point estimates of sensitivity/PPA and specificity/NPA of index test on alternative specimen types, with 95% confidence intervals, using a lab-based PCR on the corresponding sample type as reference standard		
Study design	This is a prospective, diagnostic accuracy study. The same study design is applied to each POC evaluation (sub-study) performed under this protocol.		
	Considering that the mpox outbreak situation (incidence) is subject to change, enrichment strategies to meet the study objectives may be discussed with single study sites and adopted at any time during the study, provided that specific go/no go criteria are met, and study validity and data integrity can be preserved. Potential enrichment strategies considered are:		
	
 
Including close symptomatic contacts of a confirmed mpox case through contact tracing procedures
 
Frozen lesion and respiratory samples from FIND or local sample repositories, and/or same-day, fresh left-over specimens available in the local diagnostic laboratory may be used, provided they were collected from patients meeting the eligibility criteria.
 
Additional sites may be considered.
 
		
	The procedures to be followed in case enrichment strategies are implemented will be included in the Study Manual. However, only participants enrolled and/or specimens collected after consent and/or assent will be included in the study.		
	There will be no follow-up visits. Only the reference PCR result will be communicated to the participant.		
	In order to make the information on test performance available timely, a partial analysis will be performed every time the collection of data for each RDT has been completed at one site. This analysis will evaluate the primary outcomes for a given RDT at a specific site.		

Performance evaluation of Mpox point-of-care diagnostics

Protocol #PP008 Page 13 of 40

Study sites/setting	The study will initially include 3 evaluation sites, two in endemic African countries and one in a newly affected European country:			
	- Institut Pasteur de Bangui, Central African Republic			
	- Institut National de Recherche Biomédicale, Democratic Republic of Congo			
	- Liverpool School of Tropical Medicine, United Kingdom			
	Each index test is evaluated at all study sites. Each evaluation site may recruit study participants from one or more associated clinics.			
	Additional sites may be considered should i) other POC devices become available through FIND's selection for clinical performance evaluation and/or ii) mpox outbreak situation change in the above-mentioned sites (see above).			
Study population	Individuals ≥ 2 years of age suspected to have mpox (and/or specimens collected from them), as per national or WHO case definitions.			
Sample Size	The sample size for this study is at least 30 positive and 30 negative samples for each index test evaluation based on U.S. FDA guidelines. Assuming that both the sensitivity and the specificity of the test are 90% this would result in a full width of 95% confidence interval of $\pm 11\%$ , based on the formula 6.2 in Zhou et al			
	Since the prevalence of the disease in these areas is unknown, an interim analysis will be performed to estimate the prevalence with its 95% confidence interval once the enrolment reaches 50 participants for each site. Following this, the lower bound of the confidence interval will be used to estimate the number of participants to be screened based on the formula 6.3 in Zhou et al. Assuming a lowest possible prevalence of 10%, 5%, and 1%, the number of participants to be screened to reach 30 confirmed cases with an 80% power would be:			
	
 
10% prevalence: 348 to screen
 
5% prevalence: 697 to screen
 
1% prevalence: 3496 to screen
 
			
Eligibility	Inclusion criteria			
criteria	Individual ≥ 2years of age			
	Meet case definition for a suspected case of mpox (as per national or WHO clinical case definitions)			
	
 
Provide written informed consent (by the participant or legal representative) and/or assent to participate in this study
 
			
	Provide specimens for the study			
	Exclusion criteria			
	Individual with no visible rash or lesions			
Study duration	This study is planned to take approximately 6-9 months to complete.			
Time schedule	Study preparation and IRB approvals: 3.5 months			
Site activation and training: 0.5 months				
	Enrolment and data collection: 1-4 months			
	Data cleaning/data lock and final analysis: 1 month (per site)			

Performance evaluation of Mpox point-of-care diagnostics

Protocol #PP008 Page 14 of 40

# Schedule of Activities / Sample Flow

Procedure	Day 1	Day 2+	Notes
Inclusion and exclusion criteria	Х		
Informed consent and participant enrolment	Х		Consent (by the participant or legal representative) and/or assent
Participant clinical information collection	Х		
Sample collection for reference and index test	Х		Two (2) lesion swabs, two (2) oropharyngeal swabs collected. Optional: whole blood/plasma collected.
Index test performance	Х	Х	Sample must be processed following manufacturer's instructions (immediately after collection or as per maximum time stated in the IFU).
Reference test performance	Х	Х	Reference test may be performed at a later date, depending on site's workload and sample collection time.
Reference test communicated to participant	Х	Х	
Completion of CRFs	Х	Х	Some data may become available more than 2 days later (e.g., sequencing result)
AE/SAE review	Х	Х	Limited scope, see Appendix 1

#### 1 Introduction

# 1.1 Study Rationale

Mpox is a viral disease of zoonotic origin with symptoms similar to those seen in patients with smallpox, although clinically less severe. Since the eradication of smallpox in the 70s, mpox outbreaks have been reported in multiple countries in West and Central Africa; however, the true burden is unknown (1). There are two known clades of mpox virus, one endemic in Western Africa (clade II) and one in the Congo Basin region (clade I), the latter causing more severe illness. The Democratic Republic of Congo (DRC) reports the highest number of cases per year; since 2010, over 1,500 cases and 150-250 deaths have been reported per year, with a mortality rate around 10%. Cases continue to be regularly reported in the region, sustained by sporadic zoonotic and human-to-human transmissions.

In May 2022, multiple cases of mpox were identified in several non-endemic countries (2,3). As of November 13th, 2022, there have been 79,411 laboratory confirmed cases and 50 deaths reported to WHO from 110 countries/territories in the six WHO regions, with the majority being reported from the WHO region of the Americas. This multi-country outbreak was declared a Public Health Event of International Concern by the IHR Emergency Committee on July 23rd, 2022 (4). Actual case numbers are likely to be underestimated, due to the lack of early clinical recognition of the disease in non-endemic regions, as cases are often atypical to those described in previous outbreaks, limited surveillance mechanisms, and the lack of available laboratory diagnostics, among other factors.

The aim of this study is to independently evaluate the performance of novel, rapid, point-of-care (POC) and near-POC assays for the direct detection of mpox antigens (Ag) or DNA in comparison to laboratory-based PCR, which is the current gold standard for confirmatory testing of mpox infection.

# 1.2 Background

Laboratory-based, real-time or conventional PCR on skin lesion material is the recommended method for confirmation of mpox (5). However, in regions with limited PCR testing capacity or rapid access to results, POC tests for mpox, if shown to have sufficient accuracy to aid in clinical decision-making, could contribute substantially to control disease spread and improved patient management. POC tests might provide the only source of diagnostic testing in resource limited and decentralized settings where reference testing via PCR is a challenge. POC tests may also aid in contact tracing and surveillance during a known mpox outbreak.

Certain real-time PCR assays can discriminate not only mpox virus (MPXV) from other orthopoxviruses but also the two MPXV clades described above. To date, all cases identified in newly affected countries have been identified as being infected with clades IIa and IIb (formerly the West African clade) (6).

#### 1.3 Benefit/Risk Assessment

The IVDs under investigation are considered low risk to study participants as collection of lesion and OP samples are a non-invasive procedure. This procedure will be performed by the health care professionals trained to collect skin lesion samples for the reference standard PCR test.

The probability of an adverse event (AE) or serious adverse event (SAE) occurring to a study participant to be associated with the investigational product is extremely low.

This is a diagnostic accuracy study that does not utilize test results for clinical decision making. All study personnel are made aware that the novel POC tests under study is for research purposes only and cannot be used to determine whether to initiate treatment, nor for any other clinical management decisions.

Performance evaluation of Mpox point-of-care diagnostics

Protocol #PP008 Page 16 of 40

Post-test counselling and linkage to care will be provided at study sites to enrolled participants with positive mpox status by the PCR reference test.

#### (SITE to add specific details regarding if needed)

Participants do not benefit directly from the study. Participants may be reimbursed for travel, depending on the study site. The study will benefit to society through publication of study results and provide data to inform discussions on mpox POC testing policy and use, particularly in low- and middle-income countries in the future. The development and availability of mpox tests that are accurate and adapted to POC settings will improve diagnosis and treatment of patients, facilitate studies to understand mpox prevalence and natural history, and ultimately lead to effective public health measures, vaccines and therapies.

# 2 Study Objectives and Endpoints

The objectives and corresponding endpoints of this study are described in Table 1.

Table 1. Study objectives and endpoints.

Objectives	Endpoints
Primary	
1.1 To determine the diagnostic performance of mpox POC or near-POC antigen/molecular tests (index tests) on lesion specimens vs. gold-standard PCR (reference test)	1.1 Point estimates of clinical sensitivity/positive percent agreement (PPA) and specificity/negative percent agreement (NPA) of index test, with 95% confidence intervals, using a lab-based PCR as reference standard.
Secondary	
2.1 To determine the association of index test sensitivity results with disease stage (days since onset of symptoms, e.g. acute, early, late) and Ct values (as a proxy for viral load)	2.1 Point estimates of sensitivity/PPA stratified by duration of symptoms, Ct values of the reference PCR test.
2.2 To compare performance of mpox POC test results on skin lesion specimens by the following subgroups (where information is available):	2.2 Point estimates of sensitivity/PPA and specificity/NPA with 95% confidence intervals stratified by the specified subgroups.
• Sex	
Virus clade	
Age group	

 
Vaccination status (e.g. smallpox vaccination)
 
	
Exploratory	
3.1 To determine the diagnostic performance of mpox POC and near-POC antigen/molecular tests on other specimen types (e.g. respiratory swabs, whole blood/plasma) vs. gold-standard PCR on lesion specimens	3.1 Point estimates of sensitivity/PPA and specificity/NPA of index test on alternative specimen types, with 95% confidence intervals, using a lab-based PCR on lesion samples as reference standard

Performance evaluation of Mpox point-of-care diagnostics

Protocol #PP008 Page 17 of 40

3.2 To determine the diagnostic performance of mpox POC and near-POC antigen/molecular tests on other specimen types (e.g. respiratory swabs, whole blood/plasma) vs. gold-standard PCR on the respective specimen.

3.2 Point estimates of sensitivity/PPA and specificity/NPA of index test on alternative specimen types, with 95% confidence intervals, using a lab-based PCR on the corresponding sample type as reference standard

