# 6.3 Reference Standard Test and Index Test Procedures

#### Reference test

The reference test for this study will be one of the PCR kits evaluated through the WHO (8), unless importation or supply chain issues prevent the use of any of such tests in specific settings selected for the evaluation. In this case, other comparable PCR tests might be implemented throughout the study provided they are considered equivalent in respect to the study and is a country-approved method.

The diagnostic sample for the reference test is processed by trained routine personnel according to the specific standard operating procedure (SOP) in place at the site. For remnant samples, all samples included in the study will be retested by the select PCR kit (8). The test result will be recorded in the corresponding CRF. The operator is blind to the index test result.

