**Table 6: Case predictions** 

	Reference standard classification			
Case prediction		Positive	Negative	Total
	Predicted positive	а	b	(a + b)

Performance evaluation of Mpox point-of-care diagnostics

Protocol #PP008 Page 30 of 40

Predicted negative	С	d	(c + d)
Total	(a + c)	(b + d)	(a+b+c+d)

a = True Positives	Sensitivity = a / (a + c)
b = False Positives	Specificity = d / (b + d)
c = False Negatives	
d = True Negatives	

Endpoints: See Table 1 listing objectives and endpoints

The primary and secondary endpoints will be also analysed separately for the following subgroups:

- By sex (where the information is available)
- By duration of symptoms (as a categorical value, e.g. 1-3 days, 4-7 days, >7 days from symptoms onset)
- By comparator Ct value (as a categorical variable, e.g. Ct < 35, Ct >= 35)
- By virus clade (i.e Clade I, IIa, IIb, where the information is available)
- By age group (as categorical variable, i.e. ≤17, 18-45, >45)
- By vaccination status (e.g. smallpox vaccination, where the information is available)

A final analysis will be performed per each POC test evaluated once the enrolment has been completed for all sites evaluating this test.

The endpoints on accuracy will be calculated on the PP population. Based on the distribution of the results and on the heterogeneity of results across sites, a meta-analysis approach could be used in order to estimate the pooled values of sensitivity and specificity. Details on the methodology will be provided in the SAP.

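### Endpoint 2.1 does not measure the association that objective 2.1 asks for, and a Ct split such as the example at 35 would use the collected Ct values poorly

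*Protocol*

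**What the plan says.** Table 1 (protocol section 2) sets secondary objective 2.1 as "To determine the association of index test sensitivity results with disease stage (days since onset of symptoms, e.g. acute, early, late) and Ct values", with Ct as a proxy for viral load. The matching endpoint is "Point estimates of sensitivity/PPA stratified by duration of symptoms, Ct values of the reference PCR test". The synopsis pairs the two in the same way.

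The next endpoint, 2.2, reads "Point estimates of sensitivity/PPA and specificity/NPA with 95% confidence intervals stratified by the specified subgroups". Endpoints 1.1, 3.1 and 3.2 also name 95% intervals. Endpoint 2.1 is the only accuracy endpoint that does not.

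Section 8.4.1 states that "The primary and secondary endpoints will be also analysed separately for the following subgroups". Two entries in its list matter here. Ct is to be grouped: "By comparator Ct value (as a categorical variable, e.g. Ct < 35, Ct >= 35". Symptom duration is grouped as well, with three bands as the example: up to 3 days, 4 to 7, and longer.

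The same section prescribes Wilson score intervals for sensitivity and specificity. Section 8.1 says that no hypotheses are tested. Section 8.4 leaves the detailed methods for each endpoint to the SAP. Section 10.1 says that Ct values are obtained from the reference laboratories.

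**The concern.** An association needs a quantity that compares sensitivity across levels of Ct or duration: a slope, an odds ratio or a difference, with its uncertainty. Endpoint 2.1 names none. The study could report everything that the endpoint lists and still leave objective 2.1 unanswered. A reader would have to judge by eye whether a few stratum percentages differ by more than chance.

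The categorical treatment makes this worse for Ct, which is collected as a number. One cut high in the range places few positives in the upper stratum and treats everyone below it as alike. Whether a test loses sensitivity as viral load falls is what the objective sets out to learn, so the endpoint should use the data that bear on it.

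**Working it through.** **1. The text compared.** Objective 2.1 asks for an association. Endpoint 2.1 gives stratified point estimates. Section 8.4.1 adds categories and, through endpoint 1.1 and the Wilson rule, implies an interval within each stratum. No passage names a quantity that links the strata.

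**2. Inputs from the protocol.** At least 30 positives per site for each index test (section 8.2). Three initial sites (section 3.1), so 3 × 30 = 90 positives if pooled. Planning sensitivity 90% (section 8.2). The expected false negatives are therefore 0.10 × 30 = 3 at one site and 0.10 × 90 = 9 pooled.

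**3. The plan's own figure.** The protocol gives no precision for endpoint 2.1. Its only precision figure is ±11% for the primary endpoint: 1.96 × √(0.9 × 0.1 / 30) = 0.107. It reproduces as a half-width, and it applies to all 30 positives of a site, not to a stratum.

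**4. Precision within strata (Wilson 95%).**

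- One site, three equal duration strata of 10: 9/10 gives 60–98%.
- One site, 10% of positives at Ct 35 or above (an assumption): 3/3 gives 44–100%.
- Pooled, three equal strata of 30: 27/30 gives 74–97%.

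**5. Positives above a cut at 35.** The protocol gives no Ct distribution, so I assume a normal one with mean 24–28 and SD 5.

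- Mean 24: z = (35 − 24)/5 = 2.2, upper tail 0.0139. Expected 1.3 of 90, or 0.4 of 30.
- Mean 28: z = (35 − 28)/5 = 1.4, upper tail 0.0808. Expected 7.3 of 90, or 2.4 of 30.

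**6. Information lost by the cut.** Simulated studies used this Ct distribution and a logistic sensitivity curve falling by 0.15–0.20 log-odds per cycle (assumed), calibrated to 90% overall. The comparison is a trend test on continuous Ct against Fisher's exact test at 35, both two-sided at 5%.

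| Positives | Continuous Ct | Split at 35 |
|---|---|---|
| 90 (pooled) | about 52–73% | about 7–43% |
| 30 (one site) | about 20–31% | about 1–11% |

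A linear trend over four ordered Ct bands, with 90 positives, detects it in about 38–70%, depending on the scenario and the bands.

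**7. Large gaps.** Exact Fisher power for two strata, with 10%, 20% or 50% of positives in the smaller one:

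| Sensitivities | 30 positives | 90 positives |
|---|---|---|
| 95% v 75% | 14–24% | 44–71% |
| 95% v 60% | 31–52% | 78–98% |

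**8. What a regression would give.** Roughly, SE(slope) = 1/√(n × 0.9 × 0.1 × SD²).

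- n = 90: 1/√(90 × 0.09 × 25) = 0.070. For a slope of −0.20 the odds ratio per cycle is exp(−0.20) = 0.82, with 95% interval exp(−0.20 ± 0.14), about 0.71–0.94.
- n = 30: SE 0.122, interval exp(−0.20 ± 0.24), about 0.64–1.04.

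These are somewhat optimistic, because they ignore a site factor and the small number of false negatives.

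**The case against.** **The SAP may contain the model.** Section 8.4 calls itself a summary and defers methods to the SAP. This stands as far as it goes: the lack of a regression in the protocol is no error in itself. The endpoint wording and the categorical treatment, however, are stated here. A SAP that follows them keeps the mismatch, and one that replaces them departs from the protocol.

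**Intervals are already implied.** A reader might infer that strata would be reported without any interval. The documents do not support that, because section 8.4.1 applies the primary endpoint, with its 95% interval, to the same strata. The gap lies in the endpoint's wording and in the missing association measure.

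**The cut at 35 is only an example.** This is correct. Both sets of categories are marked as examples and stand in section 8.4.1, not in endpoint 2.1. Grouping as such is not the main cause of the loss, since four ordered bands recover much of it.

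**No tests are planned.** Section 8.1 rules out hypotheses. Detection rates are used above only to show how much information is lost, and an odds ratio with an interval is estimation.

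**Ct and PCR kits.** A reader might infer that Ct will be pooled over dissimilar kits, because section 6.3 says "other comparable PCR tests might be implemented throughout the study". The documents do not support that. The allowance covers import or supply problems and kits judged equivalent. The same section asks, if possible, for one reference test at one institution per index test, and nothing states that Ct is pooled across unlike kits.

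**The protocol warns about sparse data.** Section 3.1 says that the data may not suffice for the secondary subgroup analyses. That caveat concerns the enrichment strategies and does not explain why endpoint 2.1 differs from its objective.

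**Conclusion.** The mismatch holds: objective 2.1 asks for an association, and endpoint 2.1 as fixed does not estimate one and states no interval. If the example split at 35 were used, the chance of seeing a moderate gradient in 90 pooled positives would be about 7–43%, against about 52–73% with continuous Ct. At one site it would be about 1–11% against 20–31%. The one-site case matters because section 8.5 includes secondary outcomes in the site-level analyses, although the synopsis mentions only primary ones.

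These figures rest on an assumed Ct distribution and slope, neither of which the protocol gives. They concern Ct only; no comparable gradient calculation was made for symptom duration.

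The stronger statement, that strata can hardly show any association, is not supported. It fits moderate gradients, single sites and a single high cut. With 90 positives a gap of 95% v 60% would be seen in 78–98% of studies. The primary analysis and the sample size are unaffected.

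**What to change.** In Table 1, the synopsis and section 8.4.1:

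1. Add 95% confidence intervals to endpoint 2.1.
2. Name its association measure: the odds ratio with 95% interval from a logistic regression of the index result among PCR-positives on continuous Ct, and in a separate model on days since onset where recorded as a number. Pool over sites with site as a factor, and use Firth's penalty because only about 9 false negatives are expected at 90% sensitivity.
3. Keep the strata as a descriptive table, with finer Ct bands than one cut at 35.

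If the sponsor does not want a model, reword objective 2.1 as descriptive, so that it promises no more than the endpoint delivers.

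The cost is a wording change and a small extra model per index test. Ct is already collected. The protocol does not say how duration is captured, so the model on days depends on that. The intervals will be wide, and at a single site (about 3 false negatives) the model would say little, hence the pooled analysis. No sample-size figure changes.
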